Continuous variables will be described by mean (standard deviation) or median (interquartile range (Q1–Q3)) as appropriate, while categorical variables will be presented as frequencies (percentages). Costs will be described by median (interquartile range (IQR)), and the difference between control and intervention (prehabilitation) groups, so positive values should be interpreted as savings.

The normality of distribution will be assessed with the Shapiro-Wilk Test. Between-group comparison of continuous variables and costs will be performed using either Student's *t*-test or the Mann-Whitney U test according to their distribution while Pearson's χ^2 test or Fischer's test will be used for categorical variables. Quantile regression will be used for medians. To control for the usually skewed distribution of costs, a bootstrapping analysis will be performed to increase the robustness of the analysis.

All comparisons will be two-sided, with a significance level of 0.05. All statistical analyses will be made with R version 4.0.2, (R-Foundation, Vienna, Austria) software or STATA v.17 software.

Subproject: #2

This is a prospective, randomised, open-label, controlled trial with allocation ratio 1:1 comparing standard of care versus 4–6 weeks of a multimodal prehabilitation programme. The recruitment period is scheduled from March 2018 to January 2021. Both primary endpoint and baseline data will be blindly assessed. Intention-to-treat criteria will be used in order to define the analysis population; all randomised patients will be included in the analysis according to assigned group. The study protocol and informed consent have been evaluated and accepted by the Medical Research Ethics Committee at Hospital Clinic de Barcelona (2017/0708). The trial will be conducted according to the rules of Good Clinical Practice.

METHODS AND ANALYSIS

- Setting

This trial will be conducted in a single academic tertiary hospital in Barcelona, Spain (Hospital Clinic de Barcelona). Assessments and study interventions will be performed at the outpatient ambulatory infrastructure of Hospital Clinic de Barcelona. Surgery and postoperative hospitalization will take place in the aforementioned hospital.

-Eligibility criteria

Inclusion criteria: Patients older than 18 years old scheduled for CABG and/ or valve surgery, with an expected waiting time before surgery of 6 weeks or more and that accept to participate in this clinical trial.

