After signing the informed consent all participants will undergo a full blinded baseline medical, functional, nutritional and psychological assessment. Allocation to study group will be revealed to the part of the research team that will carry out the intervention once baseline assessment is completed. The functional capacity assessment will be conducted by a physiotherapist on different days to avoid fatigue related to it, and will consist in a standard incremental cardiopulmonary exercise testing on cycloergometer (CPET), where physiological variables in response to exercise and workload in watts (W) will be measured at the anaerobic threshold and at VO₂ peak, Endurance time (ET) in seconds will be measured by a cycling constant work-rate exercise test performed at a load equivalent of 80% of the peak workload (PWR) the patient could tolerate on the incremental CPET (Ergo- line 900, Ergoline, Bitz, Germany and Ergocard Professional, Medisoft, Sorinnes, Belgium). It will detect the responsiveness of interventions in terms of improved exercise capacity.

Participants will also undergo hand grip strength test (Jamar Hydraulic Hand Dynamometer; Sammons Preston, Bolingbrook, Illinois, USA), 6min walk test (6MWT) and sit-to-stand (STS) test. The 6MWT will assess functional capacity in relation to activities of daily living. Constant work rate exercise test and 6MWT are complementary in the comprehensive evaluation of these patients. Nutritional status will be assessed by a registered dietitian using the Patient Generated Subjective Global Assessment, weight, body mass index, prealbumin and glycosylated hemoglobin (HbA1c). American Society of Anesthesiologists status, Charlson Comorbidity Index and Euroscore II data will be recorded. Physical activity will be measured by the Yale Physical Activity Survey (YPAS), functional capacity by Dukes Activity Status Index questionnaire and Anxiety and depression measured using the Hospital and Anxiety Scale (HADS). All patients will be reassessed using the same tests before undergoing cardiac surgery (T7) and at 3 months postoperatively (T9).

-Procedures

Standard of care (T1–T6): Participants in the control group will follow the standard preoperative protocol at Hospital Clinic de Barcelona that includes physical activity recommendation, nutritional and smoking cessation advice. Moreover, patients suffering from iron-deficiency anaemia will receive intra-venous iron infusion.

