Multimodal Prehabilitation programme (PreHab) (T1–T6): Participants in the intervention group will undergo, in addition to the standard of care aforementioned, a 4–6-week personalized multimodal prehabilitation programme. The interventions included will be patient-centred aiming to optimize patients' preoperative health status while enhancing their empowerment and engagement. The main components of the programme will consist in:

1. Supervised exercise training programme: 1-hour session, two sessions per week at the hospital outpatient gym facility conducted by a physiotherapist. Heart rate, blood pressure, oxygen saturation and perceived exertion rate using the modified Borg scale will be monitored throughout the training session.
 - i. Endurance training will be performed on stationary bicycle (Bike Forma; Technogym; Cesena, Italy) and will be tailored to the participants according to their PWR (baseline CPET). Each session includes 5min of warm-up and 5min of cool-down pedalling at 30%–40% of their PWR. An interval training consists in at least 5 bouts combining 2 min of moderate to high-intensity exercise (starting at 70% of PWR and progressing to 90%–100% of PWR throughout the programme) interspersed with 3min recovery periods at lower intensity (40%–50% of the PWR). Progression during the sessions will be tailored on individual basis to maximize the training effect.
 - ii. Strength training will consist in 2–3 upper (pectoralis and latissimus dorsi) and lower (quadriceps) limb exercises based on 2–3 sets of 8–12 repetitions avoiding Valsalva's manoeuvres. The training is performed in a modular training station using external load (Plurima Multistation Wall, Technogym; Cesena, Italy). At the first session, the physiotherapist obtains for each muscle group, the tolerated weight for the eight-repetition maximum test, to establish the initial weight for the strength training. The weight and/or the number of repetitions will increase every week to ensure strength progression and maximize the training effect. The strength training is performed 2 days per week (in combination with the endurance training).

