2. Promotion of physical activity and healthy lifestyle: a physiotherapist adequately trained in behavioural strategies will use motivational interviewing techniques to promote physical activity and healthy lifestyle. The motivational interview will focus on empathy, reflective listening and affirmation, and will address the patients' barriers and limitations related to physical activity, to get a change in behaviour.
3. Respiratory physiotherapy: patients will be instructed on daily breathing exercises (chest expansions, diaphragmatic respirations and deep inspirations) with a volumetric incentive spirometer (Coach 2; Smith Medical; London, UK), at least twice per day, 1–2 sets of 10–15 breathings for each exercise.

4. Nutrition counselling and supplementation: participants will meet with a registered dietitian that will assess their nutritional status and their diet based on a self-reported 3-day food diary. Nutritional teaching and a Mediterranean, well-balanced cardioprotective diet will be instructed. An adequate protein intake of 1.2–1.5 g/kg/day will be aimed to meet the European Society for Clinical Nutrition and Metabolism recommendations. If patient does not reach the recommended daily protein intake with diet, protein supplementation with whey protein (Fresubin Protein powder, Fresenius Kabi España) will be provided to reach the aforementioned daily protein intake.
5. Weekly mindfulness sessions: Patients will be invited to attend 1 weekly hourly session of Mindfulness-Based Stress Reduction conducted by a registered psychologist. It will be strongly recommended to those who reported high rates of anxiety and depression on the baseline HADS.

Compliance to the prehabilitation programme will be calculated counting the number of supervised sessions attended out of the total intended sessions. The occurrence of any exercise-related adverse events during the prehabilitation period will be recorded and will be reported immediately to the principal investigator.

Preoperative (T7) and 3-month postoperative functional assessment (T9): All participants' functional capacity will be reassessed before surgery and 3 months postoperative using ET, hand grip strength test, 6MWT and STS test. Anxiety and depression and physical activity questionnaires will be also recorded at these time points.

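### Subproject 2 does not require blinded or independent testers for the effort-dependent functional tests at T7 and T9, leaving those secondary/other outcomes at risk of tester bias

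*Combined protocol and SAP*

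**What the plan says.** The Subproject 2 design paragraph states: "This is a prospective, randomised, open-label, controlled trial with allocation ratio 1:1". It then limits blind assessment to two items: "Both primary endpoint and baseline data will be blindly assessed".

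The Baseline assessment (T0) section repeats the first item: "all participants will undergo a full blinded baseline medical, functional, nutritional and psychological assessment". It also says when allocation is disclosed, and to whom: "Allocation to study group will be revealed to the part of the research team that will carry out the intervention once baseline assessment is completed". On who tests, it says: "The functional capacity assessment will be conducted by a physiotherapist on different days". It adds that the same tests are repeated at T7 and T9.

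In the description of the prehabilitation programme, the supervised training consists of "two sessions per week at the hospital outpatient gym facility conducted by a physiotherapist". The Setting section places testing and training together: "Assessments and study interventions will be performed at the outpatient ambulatory infrastructure of Hospital Clinic de Barcelona".

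The section on T7 and T9 says that participants' "functional capacity will be reassessed before surgery and 3 months postoperative using ET, hand grip strength test, 6MWT and STS test". It does not say who runs the tests or what they may know about the arm.

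Outcomes lists these measures as other outcome variables, after the primary and secondary ones. Statistical analyses calls the change in functional capacity secondary and plans generalised estimating equations (GEE) with 95% confidence intervals.

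**The concern.** T7 and T9 are the visits at which the programme's effect on fitness is measured, and they fall after the training staff have learned the allocation. Endurance time, walking distance, sit-to-stand count and grip force all respond to how hard the patient is urged on. A tester who knows the arm, or who has trained the patient for weeks, may encourage differently without meaning to.

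A difference of that kind arises after randomisation and runs along the arms. Neither randomisation nor the GEE model can separate it from a training effect. These outcomes are the trial's direct evidence that the programme changed functional capacity, so the reader of the results needs to know whether the testers were blinded.

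**Working it through.** **1. Blinding statements in Subproject 2, by what they cover**

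| Section | Who or what is blinded | Covers T7/T9 functional tests? |
|---|---|---|
| Design paragraph | Baseline data and primary endpoint | No |
| Baseline assessment (T0) | The T0 assessment | No; for T7/T9 it carries over the tests, not the blinding |
| Surgery and hospital admission (T8) | Perioperative care staff; the collector and the reviewer of complications | No; concerns surgery, admission and complications |
| Data monitoring | Describes the trial as unmasked | No |
| Neurocognitive subproject | Cognitive testers, named at baseline | No; different tests |
| T7/T9 functional assessment | Silent | No |

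No statement covers these tests.

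**2. Separation of tester and trainer**

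A physiotherapist tests and a physiotherapist trains, in the same outpatient infrastructure. The text neither says that this is one person nor excludes it. A team that follows the plan to the letter may therefore have the trainer test the trainee.

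**3. Number analysed per arm**

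Inputs from Statistical analyses: 30% complications in controls, two-sided alpha 0.05, power 80%, 10% drop-out, 80 per group. I read the stated 20% reduction as 20 percentage points (30% to 10%), because that reproduces the plan's figure:

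- Two proportions, 0.30 against 0.10, with continuity correction: 72 per group (62 without).
- Allowing for drop-out: 72 / 0.90 = 80 per group, as stated.

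The sample size is not in dispute. It only supplies 72 as a plausible number analysed (80 × 0.90 = 72).

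**4. What a tester shift could do (illustration)**

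Assumptions, none of them from the documents: no true effect, one two-sided 5% comparison of means, and a shift of d standard deviations in favour of prehabilitation that comes from the tester alone.

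- Standard error in SD units: √(2/72) = 1/6.
- Non-centrality: d / (1/6) = 6d.
- Rejection rate: 1 − Φ(1.96 − 6d) + Φ(−1.96 − 6d).

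| d (SD) | 6d | Rejection rate, 72 per arm | Rejection rate, 80 per arm |
|---|---|---|---|
| 0 | 0 | 5.0% | 5.0% |
| 0.1 | 0.6 | 9.2% | 9.7% |
| 0.2 | 1.2 | 22.4% | 24.4% |
| 0.3 | 1.8 | 43.7% | 47.5% |

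The planned GEE analysis of change would have a different standard error, so these rates would differ under it, but it would not remove the shift.

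**The case against.** The strongest reply is that the plan tells the allocation only to the staff who deliver the intervention. If the testers are other people, the plan does not unblind them, and what is missing is one sentence. That is a fair reading, but the documents do not say that T7 and T9 testers stand outside the intervention team.

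Several stronger readings are tempting and should be resisted:

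- **That one physiotherapist does both jobs.** The text uses the same job title twice and no more. The overlap is not excluded, but it is not shown.
- **That a standing pool of blinded T0 testers exists.** Blinding at T0 may rest on timing alone, since disclosure follows that assessment; a T0 tester could be told the arm afterwards. Whether the tests can be rostered without extra staff is therefore an inference from the restricted disclosure, not a stated fact.
- **That blinding at T0 achieves little.** Randomisation precedes the consent conversation and the consent forms differ by arm, so allocation already exists at T0. Change from baseline is analysed, so blinding at T0 is a real safeguard.
- **That the functional results are biased, or cannot be used.** Silence in the plan shows a risk only.

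Two limits on the remedy also stand. Patients in the intervention arm know their programme, so blinding the tester reduces bias in effort but does not remove it. Self-reported measures such as the Yale Physical Activity Survey would gain little.

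**Conclusion.** The gap is real. As written, the plan allows T7 and T9 functional tests to be run by staff who know the arm or who trained the patient, and the between-group change in these tests is at risk of tester bias.

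The reach is limited. These are secondary or other outcomes, depending on the section. The primary endpoint is collected and reviewed by blinded staff and is not affected.

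The size of any bias is unknown. The range from 9% to 44% shows how sensitive the results would be under assumed shifts of 0.1 to 0.3 SD; it is not an estimate for this trial. The conclusion that the safeguard is missing rests on the text alone and does not depend on those figures.

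**What to change.** Add to the section on T7 and T9:

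1. The functional tests are run, within existing staff, by team members who did not train that patient and have not been told the allocation.
2. Encouragement and test instructions follow one script in both arms.
3. Any unblinding of the tester is recorded.
4. Where this rostering is not possible, the script is kept and the outcomes are reported as assessed unblinded.

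An instruction to patients not to reveal their arm is better left out, or worded neutrally. Under the two-consent design in the Informed consent section, control patients are invited to a study of cardiopulmonary reserve, and such an instruction could tell them that another arm exists.

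If testing is already complete, the report can still state who tested and whether they knew the arm.

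The cost is a few sentences and some scheduling constraint. The script and the record need no added staff. Some bias will remain, because intervention patients know their programme and some will disclose it.

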Surgery and hospital admission (T8): Surgery will take place in the habitual waiting timeframe and will be performed by the regular cardiac surgery teams present in Hospital Clinic de Barcelona. Perioperative clinical protocols will be followed in a usual fashion independently of the group allocation or study participation. Hospital staff, anesthesiologists, surgeons, nurses and other people involved in patient care will be blinded to the study arm. Intraoperative complications or events as well as the need blood product transfusion or any deviation from normal course will be recorded in the intraoperative case report form (CRF).

The primary outcome of this study is the incidence of postoperative complications before patient discharge from the hospital. The type of complications included will be classified following the standards of the European Society of Anesthesiology and the European Society of Intensive Care medicine: Acute kidney injury, acute respiratory distress syndrome, arrhythmia, cardiac arrest, cardiogenic pulmonary oedema, deep vein thrombosis, delirium, gastrointestinal bleed, infection, source uncertain, laboratory confirmed bloodstream infection, myocardial infarction, pneumonia, paralytic ileus, post-operative haemorrhage, pulmonary embolism, stroke, surgical site infection and urinary tract infection.

The severity of complications will be also recorded, as a secondary outcome measure, following the Clavien- Dindo classification. To ensure accuracy of the primary endpoint, the data will be collected by a physician member of the team, every day according to standard clinical care, and then reviewed by another researcher. Both of them will be

blinded to the study group to avoid bias. Patient- chargeable costs (ie, pharmacy and blood bank); tariff- chargeable costs (ie, medical care, diagnostic techniques, laboratories, interconsultations); other healthcare resources use (ie, ICU stay, total hospitalisation length of stay, readmissions, emergency room visits) and survival will be also assessed at 3 months and 1 year postcardiac surgery by chart review.

Data collection management and monitoring: All participant's de-identified data collected at different time points will be entered by research staff members into Research Electronic Data Capture (REDCap) CRF via a secure webpage interface. Online data will be stored in a safe server located the Hospital

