Sample size for this trial has been calculated based on the primary outcome of the study that is the reduction of incidence of postoperative complications in the prehabilitation group. Our own data in a similar population of patients indicated that the incidence of postoperative complications was 30%. Accepting a two-sided alpha-risk of 0.05 and beta-risk of 0.20, anticipating 10% of drop-outs, indicated the need of including 80 participants per group to detect a reduction of the percentage of patients with complications in the intervention group compared with the control group 20%. No adjustment for multiplicity was proposed due to this is a clinical trial with one primary outcome and without needed of interim analyses.

This trial will use intention-to-treat criteria for main analysis; nevertheless, analysis per protocol will also be performed as supportive analysis. Categorical variables, as well primary outcome, will be analysed with Fisher's exact test. Continuous variables will be compared with Student's t-test for independent groups and Mann-Whitney U test according to each variable distribution. Ordinal variables will be analysed by Mann-Whitney U test.

Secondary outcomes looking at the difference between groups for the change in functional capacity over the different time points (repeated measures) will be analysed using generalized estimating equations models and will be shown as estimated effect and their 95%CI. For these analyses, we will apply unstructured matrix in order to assess intra-subject correlation, for cases with no adjustments we will apply an autoregressive model (AR) (1) type matrix.

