A cost-effectiveness study will be carried out from the perspective of the hospital, taking into account the costs of the intervention and the expenses related to the disease during the follow-up (30 days). For costs, the mean or median and their 95%CI of difference in per-patient costs between the two groups will be computed (control-group costs minus prehabilitation-group costs), so that positive values will be interpreted as savings of the prehabilitation programme. Considering previous experience with prehabilitation cost analysis, a highly skewed distribution will probably be present. Right-sided asymmetric distribution appears when some patients incur in high costs, mainly because of major medical complications. To deal with this, a non-parametric approach (bootstrapping) will be used. Bootstrap analysis yields more robust when dealing with skewed cost data compared with non-parametric tests.

- Perioperative neurocognitive disorders subproject

Inclusion criteria: Patients included in the main study with age ≥ 50 years.

Exclusion criteria: Those applied for the main study. Additionally, reading difficulties, and non-Spanish or Catalan native speakers will also be excluded.

Baseline cognitive assessment (T0): We selected a battery of tests with input from a neurologist and a neuropsychologist – both experts on cognitive disorders. Two blinded-trained professionals ([name]) will perform the cognitive assessment in a quiet

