Statistical analysis: Randomized groups will be compared for balance on all potentially confounding baseline variables using descriptive statistics and the standardized difference (ASD), which is the difference in means or proportions divided by the pooled standard deviation. Criterion for imbalance will be an absolute standardized difference > 0.10 . Any imbalanced baseline variables will be adjusted for in all analyses below. Data transformations will be made, or non-parametric analyses used to meet model assumptions, as appropriate. Analyses will be intent to treat, with a significance level of 0.05. We will assess the efficacy of the prehabilitation program to standard care on the incidence of POCD using either Pearson chi-square test or logistic regression if there is a need to adjust for baseline imbalance in potentially confounding variables. In either case, the relative risk of developing POCD at 3-months after surgery and its 95% confidence interval will be estimated.

Patient and public involvement

Patient and public involvement was taken into consideration for the development of this protocol. A satisfaction questionnaire was given to a sample of patients who had undergone a prehabilitation programme as part of their clinical pathway before an abdominal surgery. They gave feedback about both the assessments and interventions included in this trial. As a result of their feedback we proceeded to reduce the number of questionnaires given during the assessments, as well as an assessment and intervention redesign, resulting in a more flexible schedule for the participants.

- ETHICS AND DISSEMINATION

Ethics approval for this trial has been obtained by the Ethics Committee of Clinical investigation of Hospital Clinic de Barcelona (HCB/2017/0708). This trial will be conducted according to the principles emanating from the Helsinki Declaration, with compliance to the Good Clinical Practice and the International Council for Harmonisation of Technical Requirements for Pharmaceuticals for Human Use (ICH) guidelines. Confidentiality for participants and their data will be guaranteed according to the Spanish data protection law 'Ley Orgánica de Protección de Datos de Carácter Personal' (15/1999, 13 diciembre) and the General Data Protection Regulation from the European Union (EU 2016/679).

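### Subproject #2 gives its primary outcome only an unadjusted Fisher's exact test, with no effect estimate, confidence interval or baseline covariate

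*Combined protocol and SAP*

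**What the plan says.** The primary outcome of Subproject #2 is binary per patient: "The primary outcome of this study is the incidence of postoperative complications before patient discharge from the hospital" (Surgery and hospital admission, T8). Its analysis is one sentence under Statistical analyses: "Categorical variables, as well primary outcome, will be analysed with" Fisher's exact test. The main analysis is by intention to treat, with a supportive per-protocol analysis. Nothing more is said about the primary outcome.

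Three other analyses in Subproject #2 do commit to an estimate and interval:

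- Change in functional capacity: "will be analysed using generalized estimating equations models and will be shown as estimated effect and their 95%CI".
- Costs: "For costs, the mean or median and their 95%CI of difference in per-patient costs between the two groups will be computed".
- POCD, in the neurocognitive subproject: "In either case, the relative risk of developing POCD at 3-months after surgery and its 95% confidence interval will be estimated". Logistic regression is the option there if baseline adjustment is needed.

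Under Baseline assessment (T0): "American Society of Anesthesiologists status, Charlson Comorbidity Index and Euroscore II data will be recorded". None of these scores enters the primary analysis. The rule on adjusting for imbalanced baseline variables sits in the neurocognitive subproject and covers only the analyses that follow it there.

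**The concern.** The outcome that sized the trial is specified less fully than several lesser ones. A Fisher p-value does not state how large the effect is or how precisely it is known. The effect measure and interval method are therefore left to be chosen after the data are seen, and near the significance boundary that choice can change the message.

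There is also an efficiency cost. Fisher's test is conservative at this sample size and spends only about two thirds of the nominal 5% (3.3/5 = 0.66). The trial enrols a mixed-risk population ("Patients older than 18 years old scheduled for CABG and/ or valve surgery") and records a surgical risk score that could sharpen the comparison, but the plan does not use it.

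**Working it through.** **Inputs.** From Statistical analyses: control rate 30%, a 20% reduction, two-sided alpha 0.05, power 80%, 10% drop-out, 80 per group. From the T-1 section: 1:1 randomisation with no stratification factor named.

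**1. The plan's own figure.** Read the reduction as absolute, 30% to 10%, so the mean rate is 0.20:

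- Uncorrected: n = [1.96·√(2·0.2·0.8) + 0.842·√(0.3·0.7 + 0.1·0.9)]² / 0.2² = 61.6, so 62.
- Continuity-corrected: (61.6/4)·[1 + √(1 + 4/(61.6·0.2))]² = 71.2, so 72.
- Drop-out: 72/0.9 = 80.

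The stated 80 reproduces exactly. Other readings do not: 30% to 20% needs 327 per group (348 corrected), and a 20% relative reduction needs 955 (992 corrected). The continuity correction suits a Fisher-type test.

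**2. Fisher against chi-square**, by full enumeration of two binomials. Size is at a common rate of 30%.

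| Evaluable per arm | Fisher power | Fisher size | Chi-square power | Chi-square size |
|---|---|---|---|---|
| 72 | 82.6% | 3.3% | 87.4% | 5.1% |
| 80 | 86.7% | 3.3% | 90.3% | 5.1% |

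At a common rate of 20% with 72 per arm, the sizes are 3.2% and 5.2%.

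**3. Adding one baseline score.** Simulation with 72 per arm, 30% against 10%, a normally distributed score acting on the log-odds, a logistic model on arm and score, and a likelihood-ratio test for arm (10,000 to 20,000 replicates). The score's AUC is an assumption.

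| Assumed AUC | 0.50 | 0.64 | 0.69 | 0.74 | 0.77 |
|---|---|---|---|---|---|
| Power | 87.8% | 88.7% | 89.7% | 91.5% | 92.2% |

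Type I error was 4.8% to 5.5%, and the model failed in at most 0.07% of trials. A separate simulation (5,000 replicates) gave about 88%, 91% and 94% at AUCs of about 0.63, 0.74 and 0.82.

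At AUC 0.50 the score carries no information, so the 0.4 points above chi-square (87.8 − 87.4) are simulation noise: the Monte Carlo standard error is about √(0.878·0.122/10,000) = 0.3 points, and a 20,000-replicate run of that setting gave 87.1%. The covariate gain therefore runs from zero to about 5 points (92.2 − 87.4 = 4.8) over this range. A further 4.7 points come from leaving Fisher's test.

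Mean width of the 95% CI for the risk difference: 0.251 unadjusted; 0.240 at AUC 0.69 (0.240/0.251 = 0.96, 4% narrower); 0.232 at AUC 0.74 (0.232/0.251 = 0.92, 8% narrower).

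**4. What the missing interval hides.** Take 72 per arm, with 22 control and 11 prehabilitation patients having complications:

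- Fisher p = 0.046.
- Risk difference (control minus prehabilitation): 22/72 − 11/72 = 0.153. Wilson limits are 0.211 to 0.420 and 0.088 to 0.253. Newcombe lower limit: 0.153 − √[(0.306 − 0.211)² + (0.253 − 0.153)²] = 0.015. Upper limit: 0.153 + √[(0.420 − 0.306)² + (0.153 − 0.088)²] = 0.284. So 15.3 points (1.5 to 28.4).
- Risk ratio: 11/22 = 0.50. SE of its log: √(1/22 − 1/72 + 1/11 − 1/72) = 0.330. CI: 0.26 to 0.95.

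With one fewer control event (21 against 11), Fisher p = 0.070, the Newcombe interval excludes zero (0.2 to 27.0 points), and the log-scale risk-ratio interval just includes 1 (0.27 to 1.006). The same data give different messages depending on a choice that the plan leaves open.

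**The case against.** The test matches the design: 80 per group is a continuity-corrected figure, Fisher's test exceeds the 80% target, and with no stratification factor named it ignores no design feature. All of that stands, and it is why this is not an error of validity or power.

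The covariate benefit rests on an AUC that the documents do not supply, for a composite that includes delirium, ileus and urinary tract infection. The choice of EuroSCORE II over Charlson or ASA is a judgement. This also stands. The gain can be stated only as a range whose floor is zero; at that floor, adjustment loses essentially nothing against chi-square.

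The power comparison is not at equal size: Fisher runs at 3.3%, the adjusted test at 4.8% to 5.5%. The delta-method interval covers 94.3% to 94.4% at AUC 0.69, against 95.2% for Newcombe. Much of the gain is thus unused alpha being spent, and the adjusted analysis is slightly liberal. These are real costs, though small. If all 80 per arm are evaluable, the Fisher-to-chi-square gap also shrinks to 3.6 points (90.3 − 86.7).

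Finally, severity, stay and mortality also get tests only, and any reader can compute a risk difference from two reported proportions. True, but the first point widens the gap beyond the primary outcome, and the second does not settle which measure and interval carry the conclusion, as 21 against 11 shows.

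**Conclusion.** The concern holds. The primary outcome has no prespecified effect measure, interval or covariate, and nothing elsewhere in the document supplies one. The missing estimate and interval is the firmest part and needs no assumption.

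The efficiency part has two components at 72 evaluable per arm and 30% against 10%: 4.7 points of power from Fisher's conservatism, which is exact, and zero to about 5 points from a baseline score, which depends on the assumed AUC of 0.50 to 0.77. Fisher's test remains valid and adequately powered under the plan's own assumptions. The change is worth making because it is cheap, not because the present test would mislead.

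One design feature adds some weight. Randomisation precedes the consent discussion, and the arms receive different study descriptions and consent forms (T-1 and Informed consent sections), so acceptance could differ by arm. Whether it will is unknown, and adjustment would not fully correct it.

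**What to change.** **Preferred.** Make the primary analysis a logistic regression of any listed complication on arm and EuroSCORE II (log scale), with a likelihood-ratio test for arm. Report the standardised risk difference and risk ratio with 95% CI. If the model does not converge, fall back to the unadjusted risk difference with a Newcombe 95% CI. State how a missing score is handled. Sensitivity analyses: Fisher's exact test, and the same model plus two-level surgery type (isolated CABG against any valve). Surgery type should stay out of the primary model: under assumed mixes with 40% or 60% any-valve surgery it is harmless (power 89.9% to 90.4%), but with isolated CABG at only 20%, model failures rise to 2.3% and power is 88.0%.

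**Minimum.** Keep Fisher's test and prespecify the unadjusted risk difference and risk ratio with 95% CI by named methods, and say which result governs if test and interval disagree.

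**Cost.** SAP wording only, since the score is already collected. The preferred option brings a slightly more complex model that needs its fallback (failure below 0.1% with one score), type I error of about 5% to 5.5% instead of 3.3%, and interval coverage of about 94%. Its test and interval disagree in about 0.2% of simulated trials.
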